Fifteen participants (10 completers estimating a very conservative attrition rate of 50%) will be recruited at the Tulsa Day Center (TDC), a private, non-for-profit organization in Tulsa, OK, continuously operating in the city for over 40 years. TDC offers shelter and daytime activities, including medical services, to about 250 homeless people every day. Participants will be pre-selected for participation by TDC staff based on their history of problematic behaviors (Table 1). All participants will be between 18 and 65 years of age, inclusive. TDC staff will collect information from participants regarding their diagnoses, and after initial screening, records will be obtained from clinical records to confirm psychiatric diagnosis. In addition, information regarding disruptive behaviors necessitating intervention will be obtained for the 6 months prior to enrollment to establish a historical baseline of disruptive behaviors against which the efficacy of this study intervention will be compared. Clients with a history of at least one disruptive episode per week in at least 50% of the weeks in the 6-month period will be eligible for enrollment. At this early, feasibility stage, no stratification according to sex, gender, or ethnicity will be made.

Inclusion Criteria:

1. Age 18-65 years old
2. Diagnosis of Schizophrenia Spectrum, Bipolar, or Related Disorders
3. Presence of Anosognosia (SUMD: Minimum combined score of 4 on questions 1) and 2); Recent (at least <6 months) history of disruptive behaviors (at least 1 disruptive behavior per week in >50% of weeks in the 6-month period prior to enrollment)
4. Receive case management services through TDC
5. Ability to comply with study procedures
6. Willingness to participate in contingency management intervention

Exclusion Criteria:

Based on assessment by the client's case manager, the presence of:

1. Inability to provide informed consent
2. Unstable medical conditions that would interfere with participation
3. Cognitive impairment that would interfere with participation in the study
4. History of severe aggression or violent behavior posing a risk to study staff or other participants
5. Active suicidal ideation or a history of suicide attempts within the past 12 months

D. Research Design and Methods**Description of Study Intervention:**

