- **MyHealth Access Network:** Emergency room visits, hospital visits, diagnoses, medical care, prescribed medications, etc.
- **Julotta System:** will house information on hospital admissions, arrests, case management notes, medical history, list of medications prescribed, diagnosis, insurance info, ER visits in past 12 months, 911 calls in past 12 months, push notifications, referrals to other programs, program enrollments, past employment, strengths and abilities, financial assessment, past substance abuse. Julotta access will be dependent on implementation in the local community.
- **Other community-based services** as needed (e.g. Salvation Army, social security office, etc.)

Study Duration:

The involvement of each participant in this study will last 18 months. The study will last approximately 2 years.

Outcome:

Participants will decrease the frequency of disruptive behaviors, as defined above, in comparison with the 6-month period immediately prior to recruitment.

Sample Size:

This study exploring feasibility of the CM approach to resolve social dysfunctional behaviors will include up to 15 participants with the goal to obtain 10 completers.

Description of Sites/Facilities Enrolling Participants:

Tulsa Day Center in Tulsa, Oklahoma provides of full range of services and tools to assist clients in overcoming anticipated, situational and chronic homelessness. Their priority is to address client's basic needs: shelter, food, clothing and bathing. They offer rapid rehousing services, emergency shelter, medical assistance, and legal aid to help ensure all of those needs can be met. <https://tulsadaycenter.org/>

The Blue Team initiative at Tulsa Day Center was launched in September 2022, with the primary focus of working with a subset of the homeless population in Tulsa who have difficulty obtaining and maintaining safe housing due to anosognosia.

Baseline Assessment: The initial status of participants' target disruptive behaviors will be obtained from the 6 months prior to recruitment. This information will be used as a historical, preliminary comparator to the 6 months of CM intervention.

To evaluate the inclusion and exclusion criteria, the following procedures will be implemented:

- Diagnoses will be obtained from clinical records obtained by Tulsa Day Center.

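### Fifteen enrolled, 10 completers and 50% attrition cannot all hold: 15 at 50% yields 7.5 completers, and 10 of 15 is 33% attrition

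*Protocol*

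**What the plan says.** Section C of the protocol gives enrolment, completers and attrition in one sentence: "Fifteen participants (10 completers estimating a very conservative attrition rate of 50%) will be recruited". Section D, under Sample Size, says that the study "will include up to 15 participants with the goal to obtain 10 completers" and gives no attrition rate. So 15 and 10 each appear twice, and 50% appears once.

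Under Study Duration the protocol adds: "The involvement of each participant in this study will last 18 months". If completion means finishing participation, this is the period over which dropout accrues. The protocol does not define attrition in any other way, does not provide for replacing participants who leave, and does not allow more than 15 to be enrolled.

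**The concern.** An attrition rate is ordinarily the share of enrolled participants who do not complete. On that meaning, any two of the three figures in Section C fix the third, and the third does not match what is written.

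The word used for the rate, conservative, adds to the problem. It tells the reader that 10 completers is secure against heavy dropout, whereas 10 of 15 leaves room for only five losses.

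What is at stake is the planned number of completers and how retention will be judged. Feasibility is a stated aim, and 10 completers is the only numerical sample-size goal. If 7 or 8 participants complete, the protocol supports two opposite readings: retention was as planned (50%), or the goal was missed (10). Power is not at stake, because the protocol gives no power calculation.

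**Working it through.** **Inputs**

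- Enrolled, N = 15 (Section C; a ceiling in Section D, Sample Size).
- Completers, C = 10 (Section C; the goal in Section D, Sample Size).
- Attrition, d = 0.50 (Section C only).

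**Step 1: try to reproduce the 15.** To expect C completers when a fraction d of those enrolled is lost:

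N = C / (1 − d) = 10 / 0.50 = 20.

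This does not give 15. The form that does is

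N = C × (1 + d) = 10 × 1.5 = 15,

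which takes 50% of the completers instead of 50% of those enrolled. This may be how the figure arose, but that is inference; the protocol shows no calculation.

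**Step 2: completers expected from 15 at the stated rate.**

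N × (1 − d) = 15 × 0.50 = 7.5.

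The shortfall is 10 − 7.5 = 2.5, and 2.5 / 10 = 25% of the goal.

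**Step 3: attrition implied by 10 of 15.**

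1 − 10/15 = 33.3%.

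**Step 4: chance of reaching the goal.** Assume that participants drop out independently with a common probability, so that the number of completers X is binomial (N, 1 − d). For 15 enrolled at 50%:

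P(X ≥ 10) = (3003 + 1365 + 455 + 105 + 15 + 1) / 32768 = 4944 / 32768 = 0.151, so P(X ≤ 9) = 0.849.

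The same calculation for other values:

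| Enrolled | Attrition | Expected completers | P(at least 10) |
|---|---|---|---|
| 15 | 50% | 7.5 | 0.151 |
| 15 | 37.0% | 9.45 | 0.50 |
| 15 | 33.3% | 10 | 0.618 |
| 20 | 50% | 10 | 0.588 |
| 12 | 50% | 6 | 0.019 |

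With 15 enrolled, the goal is at least as likely to be met as missed only when attrition is about 37% or lower. The row for 12 enrolled is purely illustrative. It shows what could follow because Section D treats 15 as a maximum; the protocol does not plan for 12. The row for 20 is for reference.

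**The case against.** The arithmetic is not in dispute. The case on the other side is about weight and interpretation.

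- **Nothing analytical depends on the 10.** Section G defines the primary outcome as a comparison of 6 months of intervention with the previous 6 months and does not restrict it to completers, a term the protocol does not define. Someone who leaves after month 6 could contribute the full comparison without completing 18 months. This stands, and it limits the consequence to the planning statement and the feasibility reading.
- **The 50% is probably a mislabelled allowance.** Since 10 × 1.5 = 15 exactly, the authors may have meant five extra recruits per 10 completers. On that view 15 and 10 are the real planning figures and only the rate is wrong. This is plausible, and the repetition of 15 and 10 in Section D supports it. But five extra per 10 completers is not an attrition rate of 50%, and the protocol does not say that this was meant. The second option under the fix serves this reading.
- **A conservative rate is a pessimistic bound, so the 15% chance describes a worst case.** This is fair as far as the probability goes: it applies at 50% attrition and at no other rate. It does not rescue the sentence, which presents 10 as the number obtained when 50% is assumed. If 50% is a worst case, the rate behind the 10 is not stated.
- **Enrolling 20 would keep both the rate and the goal.** That is arithmetically true, and the choice is the sponsor's. It is not needed to remove the contradiction, which can be settled within the cap of 15.

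**Conclusion.** The concern holds. The protocol's only numerical sample-size goal does not follow from its own enrolment and attrition figures: 7.5 completers are expected against 10 stated, a gap of 25%, and the rate consistent with 10 of 15 is 33.3%, not 50%. These results need only the usual meaning of an attrition rate.

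The probability of about 15% of reaching 10 also requires independent dropout at exactly 50%, which the documents do not establish; it shows the size of the gap and is not a forecast.

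This is a definite error that should be corrected. It does not undermine the design, and no power statement or decision rule changes.

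**What to change.** Decide which figure is the planning assumption and make Section C and Section D (Sample Size) agree. Two versions need no further enrolment:

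1. **Keep the rate.** Section C: 15 enrolled, with 7 to 8 completers expected at 50% attrition. Section D: change the goal of 10 to match.
2. **Keep the goal.** Section C: 15 enrolled and 10 completers, assuming attrition of about 33%, with a reason for that rate and without calling it a very conservative 50%. The goal in Section D then stays as it is.

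The cost is at most one sentence in each section, with no added participants, visits or data. The first version makes the stated number of completers less favourable. The second requires a justification for lower attrition over 18 months in this population.

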LIBR #2023-005
12/22/2023

Contingency Management for Problematic Behavior Reduction in the Community

[name].
Scientific Director and President
Laureate Institute for Brain Research
[name]
[name]
[contact]
[contact]
email: [contact]
web: <http://www.laureateinstitute.org>

Sponsor: Laureate Institute for Brain Research

Funded By: Laureate Institute for Brain Research

A. Study Purpose

This study aims to determine the feasibility and effectiveness of implementing a contingency management program in a small group of mentally ill, homeless individuals with schizophrenia or bipolar disorder and anosognosia (a lack of insight into their mental health) in the City of Tulsa. Tulsa's homeless population grew nearly 7% last year to the highest numbers since the beginning of the COVID-19 pandemic according to Housing Solutions data, an organization that oversees many of the city's efforts to address homelessness. The primary objective of the study is to decrease disruptive or problematic behaviors by homeless individuals in the community through monetary incentives.

Specific Aim: To determine the safety and efficacy of contingency management to decrease the number of disruptive events in the Tulsa community over an 18-month timeframe (e.g. interactions with police, Tulsa Fire Department, Emergency Medical SA, and 911 interventions)

B. Background and Significance

Contingency management (CM) is a behavioral intervention strategy that has demonstrated promising results in various populations. It involves the provision of tangible incentives or rewards to individuals who demonstrate specific behavioral changes, such as adherence to treatment, abstaining from drug use, or engaging in positive life choices. Whereas controversial, the employment of financial incentives to achieve behavioral goals in persons with severe psychiatric disorders has been used previously (Noordraven et al., 2017; Priebe et al., 2010; Rosen et al., 2023).

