Subjects will be selected by Tulsa Day Center (TDC) staff based on inclusion criteria. Participants will meet weekly for 30 minutes with their case manager to discuss progress on life goals and determine if the bonus payment has been earned. The participant will receive \$10 for their time spent with the case manager each week. The goal is for the participant to maintain seven

days with no disruptive behaviors (or “trouble-free days”*) per week at each visit. This goal will be verified by the case manager and lead study manager prior to the participant’s visit each week using the sources of data information described below. When the goal is achieved for a certain week, the participant will receive payment. The payment starts at \$20 and each week the amount paid per goal/week will increase by \$1. Any week with disruptive behaviors will result in returning to the \$20 baseline amount.

*“Trouble free days” definition: Trouble-free days are days during which an individual with a severe mental disorder demonstrates no occurrence of problematic behaviors and maintains a stable mental state without causing harm or disruption to themselves or others.

Table 1: Possible Sources of Data for Baseline and Ongoing Trouble-Free Day Information:

- **Homeless Management Information System:** Shows current case manager, overnight shelter stays (recorded daily), VI SPIDAT scores.
- **Vulnerability Index Service Prioritization Decision Assistance Tool (VI SPIDAT):** records self-reported periods of homelessness, evictions, emergency room visits (physical reasons), hospitalizations (physical reasons), incarcerations, crisis care admissions, hospitalizations (mental health reasons), and substance use.
- **Oklahoma State Courts Network (OSCN):** Shows legal records including evictions, arrests, charges and disposition of cases.
- **City of Tulsa Jail Hub:** Shows City of Tulsa Municipal Court charges (trespassing, erecting an abode unlawfully, etc.)
- **Tulsa Police Department:** Source for arrest records
- **Tulsa Fire Department CARES program:** Tracks number of calls to 911
- **Tulsa City and County court records:** Data base for civil commitment municipal
- **Tulsa Center for Behavioral Health:** Inpatient stays
- **Grand Addiction Recovery Center and Grand Mental Health:** Participation in recovery programs
- **Landlords:** Mental Health Association Oklahoma, Hudson Villas, Tulsa Housing Authority
- **David L Moss Inmate Search:** Arrests and charges

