The study will be terminated for the following reasons: 1) participant misses 3 consecutive case manager visits, 2) at the determination of the participant's case manager when deemed necessary for safety reasons of the participant, staff, and milieu at TDC.

By implementing this detailed CM procedure, the study will be able to assess the feasibility and effectiveness of using positive reinforcement to promote behavior change among homeless individuals with psychotic disorders and anosognosia.

G. Statistical Methods

The statistical analysis for this study will be conducted using appropriate statistical software to ensure the validity and reliability of the results. The primary goal of the analysis is to evaluate the effectiveness of the CM program in preventing disruptive behaviors among homeless individuals with psychotic disorders and anosognosia.

Descriptive statistics will be calculated for all variables, including demographics, clinical characteristics, and outcome measures. These statistics will include measures of central tendency (mean, median) and dispersion (standard deviation, interquartile range) for continuous variables, as well as frequencies and proportions for categorical variables.

To compare the intervention and control historical period, we will employ Chi-square or Fisher's exact tests for the proportion of weeks free of disruptive behaviors.

The primary outcome measure will be the proportion of disruptive behavior-free weeks in the 6 months of the intervention compared with the previous 6 months. We will use linear or logistic regression models to analyze the relationship between these outcomes and the intervention,

adjusting for potential confounding factors such as age, gender, ethnicity, and baseline clinical characteristics, including psychiatric diagnosis.

For all statistical tests, a two-sided p-value of less than 0.05 will be considered statistically significant. To account for multiple comparisons, we will apply appropriate correction methods, such as the Bonferroni or Benjamini-Hochberg procedures.

In addition to the primary analysis, we will conduct exploratory subgroup analyses to assess the intervention's effectiveness among specific subpopulations, such as individuals with different levels of anosognosia severity, specific diagnoses within the Schizophrenia Spectrum or Bipolar and Related Disorders, or varying degrees of substance use.

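### The six months that qualify a participant are also the sole comparator for the primary outcome, so the planned test cannot separate an effect of the intervention from selection

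*Protocol*

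**What the plan says.** Protocol section C has two adjacent sentences about the same half-year. The first says records for the six months before enrollment are collected "to establish a historical baseline of disruptive behaviors against which the efficacy of this study intervention will be compared". The second makes clients with "at least one disruptive episode per week in at least 50% of the weeks in the 6-month period will be eligible for enrollment". Inclusion criterion 3 repeats the rule with a strict inequality: "at least 1 disruptive behavior per week in >50% of weeks in the 6-month period prior to enrollment".

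Later sections keep that window as comparator. Section D, Baseline Assessment: "This information will be used as a historical, preliminary comparator to the 6 months of CM intervention". Section G defines the primary outcome as "the proportion of disruptive behavior-free weeks in the 6 months of the intervention compared with the previous 6 months" and names the test: "To compare the intervention and control historical period, we will employ Chi-square" or Fisher's exact test, at a two-sided 0.05 level. There is no concurrent control, run-in or second baseline.

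The stated purpose goes beyond feasibility. The Specific Aim in section A reads "To determine the safety and efficacy of contingency management to decrease the number of disruptive events", and section G makes effectiveness the primary goal of the analysis. The planned size is up to 15 participants, aiming for 10 completers.

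**The concern.** A person enters only if the baseline half-year was bad enough. Disruption-free weeks at baseline therefore cannot exceed 50%, while follow-up has no such limit. Anyone whose behavior fluctuates is more likely to be enrolled after a poor spell, and the next half-year will on average look better whether or not the payments do anything. A significant result could then be reported as efficacy when part or all of it is selection.

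The choice of test is a second problem. Ten to fifteen people contribute about 26 weeks per window. A chi-square or Fisher test on those weeks treats them as independent and the two windows as unrelated groups.

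**Working it through.** **Inputs from the protocol.** Entry at 50% or more of weeks (criterion 3: more than 50%); six months before against six months on intervention; 10 to 15 participants; two-sided 0.05. **Assumed.** 26 weeks per half-year, so entry at 13 (or 14) disruptive weeks; the six intervention months are the first six; all event rates and variances. The protocol states no expected rate, change or power for this contrast, so there is no figure of its own to reproduce.

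**1. Direction of the selection component.** Let X1 and X2 be the disruptive weeks before and after enrollment, with the same distribution (no effect, equal recording), and let c = 13. Then

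E[(X1 − c)·1(X1 ≥ c)] = E[(X2 − c)⁺] ≥ E[(X2 − c)·1(X1 ≥ c)].

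Among those selected, expected X1 is at least expected X2, whatever the dependence between windows. Selection gives an expected improvement or none, never an expected worsening.

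**2. A case that can be checked by hand.** Suppose every candidate has a weekly disruption probability of 0.4 and weeks are independent. P(X1 ≥ 13) for Binomial(26, 0.4) is 0.199. Mean disruption among those selected is 0.537; follow-up is 0.400. Spurious gain: 0.537 − 0.400 = 13.7 points. With a mean rate of 0.8 and intraclass correlation 0.1, 97% qualify and the gain is 0.4 points.

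The daily attendance of about 250 in section C does not narrow this. If 15 of 250 (6%) just qualify under the same simple model, the common rate is 0.335, baseline 0.525 and the gain 19 points.

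**3. Range under a fuller model, no effect.** logit(weekly probability) = median level + person effect (SD 0.7 or 1.0) + half-year effect (SD 0, 0.5 or 0.8; adjacent correlation 0 to 0.6). Entry at 13 of 26 weeks; n = 10 and 15; 84 settings.

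| Median weekly probability | Candidates qualifying | Spurious gain (points) | Paired-t false benefit (nominal 2.5%) |
|---|---|---|---|
| 0.2–0.3 | 5–28% | 4.7–25.3 | 18–98% |
| 0.4–0.5 | 34–54% | 2.7–15.6 | 8–66% |
| 0.6–0.8 | 64–97% | 0.4–8.6 | 2.5–27% |

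- Example A (median 0.3, SDs 1.0 and 0.5, correlation 0): 26% qualify. Disruption-free weeks go from 35% to 46%, a gain of about 10 points. At n = 15, false benefit is about 50% with the paired t and 76% with the pooled chi-square.
- Example B (median 0.7, SDs 1.0 and 0): 81% qualify. The gain is 1.2 points and paired-t false benefit 5.2%.
- Entry at 14 weeks instead of 13 adds 0.1 to 2.0 points.

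**4. Why the net direction is not fixed.** If 10% of disruptive baseline weeks go unrecorded and follow-up is complete, Example A falls to +5.3 points and Example B to −5.8. Missed follow-up events push the other way: at mean rate 0.6 and intraclass correlation 0.2, the gain is +1.7 with equal recording and +16.0 if only 80% of follow-up disruptive weeks are detected. These loss rates are assumptions.

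**5. Pooled test without selection.** Two-sided error of the chi-square on pooled weeks is about 3–5% if half-years do not vary within a person, and about 14–32% if they do (SD 0.5 to 0.8 logit).

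**6. An earlier window as comparator.** If selection used only months −6 to −1, setting months −12 to −7 against months +1 to +6 would leave a mean gain within 0.2 points. Section C, however, also has site staff pre-select on behavioral history with no time limit. Under an assumed extra screen of 26 or more disruptive weeks in 52, that contrast shows about 0.4 points in Example B, 3.6 in Example A (10% false benefit) and 12 at median 0.2 with SDs 0.7 and 0.8 (about 40%).

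**The case against.** The strongest defence is context. This is an early feasibility study of up to 15 people, the single-arm before-and-after design is disclosed, and section D calls the comparator preliminary. That limits the practical consequence, but the Specific Aim names efficacy and section G attaches a 0.05 test to this contrast. The sensitivity analyses in section G (possibly multiple imputation or propensity matching) and the covariate adjustment do not remove selection on the baseline without a control series or an unselected window.

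The bias may also be trivial. If nearly all candidates are stably disruptive in 70–80% of weeks, the gain is 0.4–1.2 points and false benefit 3–5%. That stands; the protocol neither shows nor excludes it.

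Three stronger readings are tempting but not supported:

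- A reader might infer that the result must be biased toward benefit. Only the selection component has that direction. Recording differences and losses under the termination rule in section F could change the net.
- A reader might infer that baseline is recorded less completely, since on study "This goal will be verified by the case manager and lead study manager prior to the" weekly visit. That check uses Table 1, which is headed as serving baseline and ongoing data alike. A recording gap is possible, not stated.
- A reader might take months −12 to −7 as an unselected comparator. Staff pre-selection has no time limit, so this is not established.

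On clustering, section G does not spell out how weeks are pooled and also plans regression. The point holds for the named test applied to weeks, and is separate from selection.

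**Conclusion.** The point holds and should be fixed. One window serves both as entry filter and as sole comparator, so the planned test cannot separate an effect of the intervention from selection. With no effect and equal recording, the selection component runs from about 0.4 to 25 points under the assumed rates, with paired-t false benefit of about 2.5% to 98%. Its direction follows from the entry rule given windows with the same distribution; its size rests wholly on assumed rates and variances. The net bias, after recording differences and attrition, is undetermined in sign. It does not follow that the intervention is ineffective or that an observed improvement would be spurious; the contrast cannot tell. Feasibility conclusions are untouched.

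**What to change.** 1. In section G, replace the chi-square/Fisher test on weeks with a per-participant paired analysis. Report the change from the six months before enrollment as descriptive, label it as affected by selection on the same window, and draw no efficacy conclusion from it. Pairing deals with the clustering, not with the selection.
2. Report how many candidates staff considered and how many met the 50% rule. A low share warns of a large selection component.
3. Score the outcome in both windows from the same Table 1 sources, extracted in the same way.
4. Optionally, show months −12 to −7 as a descriptive sensitivity comparison where records cover both windows equally. It must not be the sole basis for an effectiveness statement.
5. Reconcile the two wordings of the entry threshold in section C.

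Items 1 to 3 need a wording amendment, a change of test, a screening count and one uniform record extraction, with no extra participants or visits. Item 4 needs a 12-month look-back, and some participants may lack usable earlier records. The real cost is a weaker statement: the apparent improvement can no longer be presented as a tested effect.

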- Anosognosia Assessment: Utilize standardized instruments such as the Scale to Assess Unawareness of Mental Disorder (SUMD) to evaluate the presence of anosognosia in potential participants.
- Legal Involvement and Impulsive Behaviors: Review participants' legal records and self-reported incidents within the past six months to assess their history of legal involvement or impulsive behaviors.
- Housing Status Assessment: Obtain information on participants' housing history through self-report or case management records to determine the stability of their housing situation over the past six months.
- Informed Consent: Ensure participants can provide informed consent by assessing their understanding of the study's purpose, procedures, risks, and benefits through a written or verbal quiz.
- Study Procedures Compliance: Assess participants' willingness and ability to comply with study procedures during the screening and informed consent process.

- Participation in Other Interventions: Inquire about potential participants' involvement in any other intervention studies targeting the same population or addressing similar issues.

Clinical and Demographic Information

- Age
- Race/ethnicity
- Gender
- Psychiatric diagnosis
- Legal history
- Housing status
- Medical, mental health and substance use treatment history
- Housing/shelter
- Legal involvement
- Participation in programming
- Emergency Medical Services Authority (EMSA) visits
- Community Outreach Psychiatric Emergency Services (COPES)

Interview and Self-Report Questionnaires

The Scale to Assess Unawareness of Mental Disorder (SUMD): The SUMD has been validated in schizophrenia and schizoaffective disorder and uses a structured interview administered by trained raters. The SUMD derives from Amador's complex model of (Dumas et al. 2013) and includes a symptom checklist in addition to general items related to awareness of illness, attribution of symptoms to a mental disorder, awareness of effects of medication, and awareness of social consequences of illness. Furthermore, SUMD scoring includes subscales that relate the general items to specific symptom constellations.

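### Baseline and follow-up weeks are not held to one definition, timing and source list, so measurement alone could move the primary before-after contrast in either direction

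*Protocol*

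**What the plan says.** Protocol section G defines the endpoint: "The primary outcome measure will be the proportion of disruptive behavior-free weeks in the 6 months of the intervention compared with the previous 6 months". There is no concurrent control group.

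For the baseline window, section C says that "information regarding disruptive behaviors necessitating intervention will be obtained for the 6 months prior to enrollment to establish a historical baseline". The screening procedures in section D add a further input: "Review participants' legal records and self-reported incidents within the past six months to assess their history of legal involvement or impulsive behaviors".

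For the intervention window, section D (Description of Study Intervention) sets a goal of seven trouble-free days per week. On checking it, the protocol says "This goal will be verified by the case manager and lead study manager prior to the participant", and places the check before the "visit each week using the sources of data information described below". A trouble-free day is one on which the person "demonstrates no occurrence of problematic behaviors and maintains a stable mental state without causing harm or disruption to themselves or others".

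Table 1 is headed "Possible Sources of Data for Baseline and Ongoing Trouble-Free Day Information". One entry carries a condition: "Julotta access will be dependent on implementation in the local community". The last entry adds other community services as needed. The Outcome paragraph in section D compares disruptive behaviors with the preceding 6 months and refers back to a definition given above it.

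**The concern.** In a trial whose only contrast is before against after, any change at that boundary in how a week is scored is mixed with the effect of the intervention. No significance test can separate the two, and the sensitivity analyses for missing data in section G cannot recover events that were never looked up.

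Three features of the text differ, or are free to differ, across the boundary.

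- **What counts.** Baseline is worded as behaviors that needed intervention. The follow-up definition does not require intervention and adds mental stability. Most Table 1 sources record events such as arrests, charges, 911 calls and admissions. They would seldom show a past week of instability that led to no event.
- **When it is looked up.** Baseline is searched after the fact. A follow-up week is checked before that week's visit, and no later re-check is described for records that post afterwards.
- **From what.** The list is shared, but nothing fixes which of its sources must be used in both windows.

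**Working it through.** **The two windows side by side**

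| | Baseline (6 months before) | Intervention (6 months) |
|---|---|---|
| Event | Behavior that needed intervention (section C) | Any problematic behavior, or loss of mental stability (section D) |
| Timing | Look-back over the whole window | Weekly, before the visit |
| Sources | Table 1, possible sources; self-reported incidents named at screening | Table 1, possible sources; Julotta conditional |
| Who | Not named for the event count | Case manager and lead study manager |
| Late records | Included if posted by the search | No re-check stated |

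**Size.** The protocol gives no detection rate, effect size or power, so there is no figure of its own to reproduce. What follows is an illustration.

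Inputs from the protocol: 10 completers, 6 months taken as 26 weeks per window, two-sided 0.05 (so 2.5% nominal in the direction of improvement).

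Assumptions: no true change; true free share p = 0.35 (eligibility asks for disruption in at least half of the weeks, so p is at most about 0.50); between-person SD 0.10 (beta distribution); every disruptive baseline week detected; paired t-test on person-level counts. The test is deliberately a sound one, so that the result isolates measurement.

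Let m be the share of disruptive follow-up weeks missed. The spurious gain is (1 − p) × m:

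- m = 0.05: 0.65 × 0.05 = 0.0325
- m = 0.10: 0.65 × 0.10 = 0.065
- m = 0.20: 0.65 × 0.20 = 0.130

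Now let e = 0.10 of otherwise free follow-up weeks fail on mental state alone. There are two ways to apply this.

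(a) To truly free weeks only, the shift is (1 − p)m − pe, with pe = 0.35 × 0.10 = 0.035:

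- 0.0325 − 0.035 = −0.0025
- 0.065 − 0.035 = +0.030
- 0.130 − 0.035 = +0.095

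(b) To all weeks that look free, the shift is [p + (1 − p)m](1 − e) − p:

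- 0.3825 × 0.9 − 0.35 = −0.006
- 0.415 × 0.9 − 0.35 = +0.0235
- 0.48 × 0.9 − 0.35 = +0.082

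Share of simulated trials falsely showing improvement (40,000 trials per setting, 10 people):

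| Missed in follow-up | Missed records only | Plus 10% loss, (a) | Plus 10% loss, (b) |
|---|---|---|---|
| 5% | 11% | 2% | 2% |
| 10% | 29% | 9% | 7% |
| 20% | 77% | 51% | 40% |

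With equal detection in both windows the rate returns to about 2.5%. Two further settings:

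- No missed records and the 10% loss alone: the shift is −3.5 points, and about 12% of trials falsely show worsening.
- Baseline also misses 5% while follow-up misses 10%, no mental-state loss: the gain is 0.65 × (0.10 − 0.05) = 0.0325, and false improvement is about 10%, not 29%.

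**Cross-check with the planned type of test.** Use a chi-square test on 10 × 26 = 260 person-weeks per window, treated as independent, with half of weeks truly disruptive and full baseline detection. Follow-up detection of 90%, 80% or 70% gives apparent free shares of 55%, 60% or 65% against 50%. The test rejects in about 21%, 63% or 94% of trials.

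**The case against.** The strongest reply is that the protocol means to measure both windows alike. Table 1 is a single list for baseline and ongoing data. The Outcome paragraph points to one definition. The weekly goal is itself phrased as days without disruptive behaviors, and the payment reset is triggered by disruptive behaviors. This stands as far as intent goes: the definition problem is an inconsistency in wording, not two declared outcome rules. It does not settle the matter, because the definition that precedes the Outcome paragraph is the trouble-free-day one, and the baseline wording in section C does not match it.

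Several stronger readings are tempting and should not be drawn.

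- **That the case manager alone judges follow-up weeks.** The sentence names the lead study manager as well and ties the check to listed sources.
- **That different sources are planned.** They are not. Differences are only possible, because the list is not binding and Julotta is conditional. Julotta's listed content includes 911 calls and emergency visits over the past 12 months, so it might cover both windows, and other sources overlap with it.
- **That payment decisions are stated to be the analysed data.** The protocol never says so outright. It describes no other follow-up scoring, so this is the natural reading, but it remains an inference.

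The lag argument also has limits. No posting delay is stated. Baseline weeks just before enrollment face nearly the same lag as follow-up weeks, and a disruptive week is missed only if every event in it is missed. Finally, the protocol itself calls the baseline a preliminary historical comparator in a feasibility study of up to 15 people. That tempers the weight of the point, but a test at 0.05 is still planned on this contrast.

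Extraction detail can be left to an analysis plan or manual. What counts as an event and when it is looked up are already written in this protocol, and they are written differently for the two windows.

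**Conclusion.** The point holds in a limited form. As written, the protocol does not score the two halves of its primary comparison the same way, and a difference produced by measurement alone is possible. Its sign cannot be determined from the document: checking before late records arrive would favor the program, while the broader trouble-free-day definition would count against it.

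A reader might infer from the 77% figure that the design is biased toward success. The protocol does not support that. The figure needs 20% of disruptive follow-up weeks missed, none missed at baseline and no offsetting loss. All miss and loss rates here are assumptions. Across the settings shown, false improvement ranges from below nominal to about 77%, and the net shift from −3.5 to +13 points. What can be said firmly is that neither a positive nor a null result could be read cleanly without equal ascertainment. The change should be made. It is not a reason to stop the study.

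**What to change.** Keep the weekly verification for deciding payment only. For the primary outcome, state in the protocol that:

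1. Both 26-week windows are scored by one record-based event definition. Reconcile the section C wording on behaviors that needed intervention with the section D trouble-free-day definition, and leave the mental-stability element out of the primary outcome.
2. One fixed list of sources is used, limited to those that cover both windows for that participant. Julotta is left out where it covers only one window.
3. Records are pulled at the same fixed lag after each window closes. The baseline count for analysis then comes from that pull, separately from the screening count used for eligibility.
4. The lead study manager, already named in the protocol, scores both windows.

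The cost is protocol wording and one extra record pull per window for each participant, with no new staff. The small loss is that events known only to the case manager leave the primary outcome. They can be reported separately.
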